## Abbreviations and Definitions

AE	Adverse Event
ANCOVA	Analysis of Co-Variance
CI	Confidence Interval
CRF	Case Report Form
EoI	End of Intervention
FACT-C	Functional Assessment of Cancer Therapy - For patients with Colorectal cancer
FACIT-Fatigue	Functional Assessment of Chronic Illness Therapy-Fatigue
HADS	Hospital Anxiety and Depression Scale
NHS	National Health Service
RCT	Randomised Clinical Trial
SAP	Statistical Analysis Plan
SPAQ	Scottish Physical Activity Questionnaire

## **Introduction**

### **Preface**

The research question is: Is using an existing cardiac rehabilitation service delivered by a cardiac multi-disciplinary team (e.g. cardiac physiotherapist, cardiac nurse) with support from a cancer-exercise specialist, to mixed classes of cancer/cardiac patients (with some components tailored to meet cancer patients' needs and delivered by a cancer nurse), an acceptable model of rehabilitation to aid the recovery of colorectal cancer patients? Our ultimate aim was to conduct an RCT of the clinical and cost effectiveness of utilising an existing cardiac rehabilitation service versus usual care (no routine NHS rehabilitation provision) to aid the recovery of colorectal cancer patients. Given the uncertainties surrounding such an RCT, we proposed to conduct a pilot RCT with embedded feasibility study to inform the design and conduct of a larger scale trial for which separate funding would be required. In this proposed preliminary study, we were seeking to undertake a phased programme of work comprising of intervention testing and feasibility work (Phase 1) and a pilot trial with a process evaluation (Phase 2) within the context of planning a definitive large scale RCT. We also piloted an economic evaluation because interventions have a cost component that needs to be considered when evaluating the effectiveness of the intervention to reduce the burden of a disease.

### **Purpose of the analyses**

This SAP describes the analysis of the pilot RCT Phase II data. It will compare intervention versus control. to provide data to the planning of a larger RCT, and will be included in the clinical study report.

### **Objectives and Endpoints**

#### **Study Objectives**

- To determine eligibility, consent, recruitment and retention rates and speed of recruitment.
- To determine likely contamination across trial arms.
- To determine completion rates for proposed outcomes measurement tools at baseline and follow up.
- To provide data for sample size calculation for a definitive RCT.
- To test intervention fidelity according to study protocol.
- To assess the extent to which intervention and trial procedures can be integrated into routine clinical practice.

- To conduct a preliminary economic evaluation of the cancer rehabilitation programme.

## **Endpoints**

### **Primary outcome: physical activity**

Physical activity was assessed using the Actigraph GT1M accelerometer (Actigraph LLC, Pensacola, Florida). Participants were asked to wear an accelerometer for 7 days on 3 occasions (T0 - before patients are randomised to the intervention or control group; T1 - at the end of the intervention (data will be collected 12 weeks after baseline for patients in the control arm); and T2 - 3 months later). Physical activity was also assessed subjectively using the Scottish Physical Activity Questionnaire (SPAQ) to ascertain the types of activities participants engaged in.

### **Secondary outcomes**

Quality of life: EQ-5D was used to measure quality of life.

Anxiety and depression: The Hospital Anxiety and Depression Scale (HADS), which consists of 14 questions, 7 for anxiety and 7 for depression, was used to measure anxiety and depression

Fatigue: The Functional Assessment of Chronic Illness Therapy Fatigue (FACIT-F), which is a 13-item fatigue FACT subscale, was used to measure cancer-related fatigue.

Cancer Specific Quality of Life was assessed using the Functional Assessment of Cancer Therapy – Colorectal (FACT-C) Questionnaire.

Physical activity self-efficacy, which is the belief that one can engage in, and meet physical activity goals, was also measured.

According to the behaviour motivation hypothesis, perceived risk is positively and directly related to health behaviour. Risk perception of suffering from diseases has been found to play an important role in the development of intentions to perform physical activity among older adults and in explaining cancer-related behaviours. Given the lack of agreement about quality of methods of measuring cancer risk perception, we included absolute (i.e. estimation of personal risk) and comparative measures (i.e. comparison of personal risk to other people's risk). We also included conditional (i.e. rating the probability that a certain event (e.g. cancer recurrence) will occur given their adaptive behaviour (e.g. increasing physical activity) is, or is not, performed) and unconditional (i.e. rating the probability that a certain event will occur without specifying the adaptive behaviour) measures.

## **Study Methods**

## **General Study Design and Plan**

The intervention was rehabilitation for colorectal cancer patients in a cardiac rehabilitation setting. An 8/12-week (number of weeks depending on research site) post-hospital rehabilitation programme was delivered by a member of the cardiac multi-disciplinary team (e.g. cardiac physiotherapist, cardiac nurse or dietician) to a mixed class of cancer/cardiac patients in a cardiac rehabilitation setting with some components specifically tailored for cancer patients and delivered by a cancer nurse. Rehabilitation classes were delivered twice weekly or once a week depending on research site. The rehabilitation programme comprised of 60/90 minutes (depending on research site) of exercise training (aerobic and muscle strengthening) delivered to a mixed class of cancer/cardiac patients by a cardiac physiotherapist.

Participants set individual physical activity goals with advice and support from the physiotherapist.

The exercise class was followed by 30/60 minutes (depending on research site) of education (e.g. stress management, diet, drug therapy, smoking cessation, benefits of exercise and relaxation). A colorectal cancer nurse delivered some educational sessions (e.g. cancer therapies) to cancer patients. These educational sessions were either be delivered to a group of cancer patients or one-to-one by telephone

Patients randomised to the control arm of the pilot received 'Staying healthy after bowel cancer' booklet by Bowel Cancer UK, which includes a section on 'staying fit'.

Outcome and process measures were administered on three occasions: i) T0 - before patients were randomised to the intervention or control group, ii) T1 - at the end of the intervention (data was collected 12 weeks after baseline for patients in the control arm) and iii) T2 - 3 months later. Participants were asked to wear an accelerometer for 7 days on 3 occasions (T0 - before patients were randomised to the intervention or control group; T1 - at the end of the intervention (data was collected 12 weeks after baseline for patients in the control arm); and T2 – 3 months later.

## **Randomisation and Blinding**

Patients were randomised to the intervention or control group after they consented to participating in the study and after baseline primary and secondary measures were collected. Randomisation with stratification by centre was conducted by Tayside Clinical Trials Unit. Due to the nature of the intervention, the trial was not blinded.

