6.7.4 Intervention and control

Participants will either receive rehabilitation (intervention group) or a 'Staying healthy after bowel cancer' booklet by Bowel Cancer UK (control group), as described in Section 6.4 above. However, we may make slight modifications to the intervention based on the findings of the feasibility study, which will be documented. To optimise intervention fidelity [53], interventionists will be expected to follow the cancer patient rehabilitation pathway (see Appendix 1) for this study and their site-specific rehabilitation programme. To meet Objectives 6 and 9, a researcher will contact participants randomised to the rehabilitation group each week by telephone in order to complete an intervention record log to document for example, type and duration of exercises completed and content of educational classes attended for participants receiving the intervention. A researcher will also contact participants randomised to the control group to record for example, any advice given about exercising.

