8. PLAN OF INVESTIGATIONS AND TIMETABLE																									
Key stages, milestones and outputs	-	-	-	-	1	2	3	4	5	6	7	8	9	10	11	12	13	14	15	16	17	18	19	20	21
NHS Ethics and R&D approvals (i.e. before study starts)																									
Prepare all study materials (e.g. information sheets forms and logs)																									
Appointment of Research Fellows																									
1 st Steering group meeting																									
PHASE 1																									
Cancer-exercise training for cardiac physiotherapists & evaluation forms																									
completed																									ŀ
Cancer clinicians, recruit and refer 12 cancer patients for rehabilitation																									
Researcher completes screening and recruitment logs																									
Researcher administers questionnaires and accelerometer																									
Patients attend rehabilitation (intervention)																									ŀ
Researcher telephones cancer patients and completes intervention logs																									
Researchers conducts interviews with 12 cancer patients																									
Researcher recruits 6 cardiac patients and conduct interviews																									
Researcher recruits 6 clinicians and conduct interviews																									
Researcher and Tayside CTU conducts analysis and prepares report																									
2 nd steering group meeting																									
Investigators use Phase 1 report to prepare for Phase 2																									
PHASE 2																									
Cancer clinicians recruit, and refer cancer patients for rehabilitation																									
Researcher completes screening and recruitment logs																									
ı ,	esearcher administers questionnaires and accelerometer (baseline – T0)																								
Tayside CTU randomises participants to intervention or control groups																									
Patients attend rehabilitation (intervention)																									
Researcher telephones cancer patients and completes intervention logs																									
Researcher administers questionnaires and accelerometer (follow up T1)																									
Researcher administers questionnaires and accelerometer (follow up T2)																									
Researcher conducts 24 interviews with patients & 12 with clinicians																									ŀ
Researcher and Tayside CTU conducts analysis and prepares report	conducts analysis and prepares report																								

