12.2.2 Non-staff research costs

We are requesting non-staff research costs: i) 70 accelerometers and belts (£18,760); ii) Travel: 66 interviews (£10 per participant) = £660; iii) Transcription for 66 interviews (£70 per tape) = £4,620; iv) Travel and subsistence for Advisory Group meetings = £4000; v) printing of information sheets, etc. = £1000; vi) 3 audio recorders at £70 each RA in each research site to audio-record interviews (£210); vii) 3 laptop computers at £800 for each RA in each research site to email and complete all paperwork will conducting fieldwork (£2400); viii) TCTU non-staff costs include committee travel (£1000), equipment (£800), randomisation (£1000), archiving £1000); ix) Conference fees and subsistence for NCRI annual conference and World Cancer Congress to disseminate findings (£3500); x) Costs for three members of the team to attend NIHR 'welcome meeting'. Flights from Edinburgh to Southampton are approximately £140 return. Assuming an overnight stay (£100), travel costs to and from airports (£60) and subsistence (£20), we are requesting £1000; xi)The two patient advisors will provide 18 hrs each to contribute towards designing the information for study participants, assisting in interpreting research findings and dissemination. These are costed at Grade 6.26 (£720); xii) One patient from Cardiff has been costed for 6 days to cover costs involved with patient involvement in the project (£600); xiii) 3 cancer CNSs to screen patients to determine eligibility to participate. (total 24 hours @ £25.08, £1806).

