## **Efficacy Analyses**

Scoring for outcomes follows the scoring instructions given for each questionnaire. Where no such instruction is present, the following approach will be taken:

If no more than 20% of questionnaire items are missing, the missing items will be replaced by the mean of the remaining items to build a sum score. Where more than 20% of the items are missing, the sum score will be set to missing.

Data for continuous outcome measures will be assessed for normality prior to analysis. Transformations of the outcome variables will be used where necessary if these are not normally distributed.

Outcomes will be analysed as baseline versus end of intervention (EoI) and baseline versus 3 months after intervention.

Continuous outcome will be using multiple linear regression (i.e. analysis of covariance, ANCOVA). Intervention effect differences will be reported with 95% confidence intervals (CIs) and p-values. The baseline characteristics will be explored for meaningful differences between trial arms. Where these are considered meaningful and important these variables will be entered into a stepwise selection procedure and the primary analysis will be adjusted for these variables if they are statistically selected (usual criteria  $p < 0.05$ ).

Outcome measurements across multiple study visits (baseline, EoI, 3 months) will also be analysed using mixed effects (repeated measures) regression models. Models will include fixed effects for intervention group, time point, and their interaction, plus random effects for each subject to account for repeated measures, and will assume a general covariance structure. Each model will also include fixed effects for baseline values of the outcome, other covariates, in the same way as described above for ANCOVA models.

Ordinal and binary outcomes will be analysed as described above using logistic regression.

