## **Technical Details**

All analysis will be performed using SAS 9.3. All data, analysis programs and output will be kept on the Mackenzie Server and backed up according to the internal IT SOPs.

Analysis programs will be required to run without errors or warnings. The analysis programs for outcomes will be reviewed by a second statistician, and any irregularities within the programs will be investigated and fixed and date of finalised analysis programs will be signed and recorded.

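### The reason given for not blinding does not cover accelerometer processing or statistical decisions, which the SAP leaves to judgement with nothing to keep allocation out of view

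*SAP*

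**What the plan says.** On blinding, SAP Randomisation and Blinding has one sentence: "Due to the nature of the intervention, the trial was not blinded". Section 6.7.3 of the protocol covers the timing of randomisation, stratification by centre and the trials unit responsible. The protocol text available says nothing about masking anyone.

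On analysis, SAP Efficacy Analyses provides for outcomes to be transformed if they are not normal, without a criterion. Baseline characteristics are compared between arms, and "Where these are considered meaningful and important these variables will be entered into a stepwise selection procedure" at p < 0.05. SAP Primary Efficacy Analysis lists nine candidate confounders, in addition to baseline value, group and hospital. The primary outcome is accelerometer minutes in four categories (light, moderate, vigorous, sedentary). Neither document defines a valid day, minimum wear or cut-points, or says who processes the files.

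Two safeguards are stated. Analysis follows database lock (SAP Timing of Analyses), and "The analysis programs for outcomes will be reviewed by a second statistician" (SAP Technical Details). Protocol section 8 has the researcher and the trials unit carry out the analysis, and the same unit randomises.

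**The concern.** A rehabilitation class cannot be hidden from those who attend or teach it. That is no reason for the person who decides which accelerometer days count, or whether to log-transform, to know the arm. Where such decisions are open and allocation is visible, a preference can enter without anyone intending it, and a later reader cannot rule it out.

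The covariate rule is the most exposed, because it cannot be run without looking at the arms: its first step is a judgement about which baseline differences between them matter.

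At stake are the effect estimates, confidence intervals and p-values that the SAP will report. Its Sample Size section says that the estimated intervention impact will inform the size of the definitive trial.

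**Working it through.** The documents give no figure to reproduce here, because the pilot has no power calculation. The check is therefore a comparison of roles, followed by one illustration.

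**Does the stated reason reach each role?**

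| Role | Does the nature of the intervention prevent masking? | What the documents say |
|---|---|---|
| Patients, class staff | Yes | Unblinded |
| Researcher collecting T1 and T2 | Not in itself, but the design makes it hard | The same role makes the weekly log calls |
| Accelerometer processor | No | Not identified; no wear rule |
| Statistician | No | Judgement on transformation and covariates; no masking described |

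**Do the stated safeguards fill the gap?** Locking the database stops data changing; it does not hide the arm. Program review checks that code is right; it does not limit which model was chosen.

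**Can the arm leak without the arm variable?** Yes. T1 falls at the end of an 8- or 12-week programme for the intervention arm, while "data was collected 12 weeks after baseline for patients in the control arm". At an 8-week site, T1 can differ by up to 12 − 8 = 4 weeks between arms, before any wait for a class. Visit dates must be removed as well.

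**Illustration of what open choice could do.** All inputs below are assumptions except the planned 66 patients, their split by site and the count of nine covariates.

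- No true effect. 66 analysed (14, 26 and 26 by site) or 52 analysed (12, 20 and 20).
- Log-scale outcome = 0.5 × baseline + nine independent covariates jointly explaining 5% or 20% of variance + noise. The raw outcome is exp(0.8 × that value), so it is skewed.
- ANCOVA with baseline, arm and hospital.
- Models available: 2 scales × (no added covariate, or one of 9) = 2 × 10 = 20.
- Chance of a result favouring the intervention at one-sided 0.025, with 3,000 replicates per row.

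| Analysed | Covariate share | Pre-set model | One of 20, picked without regard to arm | Most favourable of 20 |
|---|---|---|---|---|
| 66 | 5% | 2.9% | 2.5% | 6.3% |
| 66 | 20% | 3.1% | 3.2% | 7.6% |
| 52 | 5% | 2.6% | 2.3% | 6.3% |
| 52 | 20% | 2.7% | 2.4% | 6.9% |

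Simulation error is √(0.025 × 0.975 / 3000) ≈ 0.3 points near 2.5%, and √(0.07 × 0.93 / 3000) ≈ 0.5 points near 7%. A choice made without regard to arm stays close to the nominal rate. The most favourable choice roughly doubles it or a little more (6.3 / 2.9 ≈ 2.2; 6.9 / 2.7 ≈ 2.6).

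**The case against.** The strongest reply is that the weakness is loose pre-specification rather than blinding, in a pilot whose main products are rates and variability. Much of this stands. Covariate choice does not touch recruitment, consent or retention. Hiding the arm does not cure stepwise selection; a list fixed in advance does. Hence the fix replaces the rule as well as masking it.

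Four stronger readings are tempting, and the documents do not support them.

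- *T1 and T2 questionnaires could have been masked at no cost.* Protocol section 6.7.4 states that "a researcher will contact participants randomised to the rehabilitation group each week by telephone in order to complete an intervention record log", and "A researcher will also contact participants randomised to the control group to record for example, any advice given about exercising". In the section 8 timetable the same role appears again: "Researcher administers questionnaires and accelerometer (follow up T1". The equipment budget ("3 laptop computers at £800 for each RA in each research site") suggests one research assistant per site. Conversations about the classes therefore precede T1 by design. The staffing-cost text was not available, so whether separate collectors were affordable cannot be judged.
- *Interviewers influenced the answers.* The documents do not state how the questionnaires were completed, and self-completion may already have been the practice. In any case patients know their arm, so no masking of staff removes bias in their own reporting on SPAQ, EQ-5D, HADS, FACIT-F or FACT-C.
- *The analyst knew the allocation and decided valid wear.* The documents show no rule, no named processor and no masking. They do not show what was done.
- *The SAP carries a false-positive rate of 6% to 8%.* That column assumes someone always takes the best of 20 models. The SAP's own procedure is different, and nothing suggests such conduct.

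**Conclusion.** The concern holds for processing and analysis only. A single reason is applied to the whole trial, yet it does not explain why wear, transformation and covariate decisions should be open to someone who can see the arm. The written safeguards do not close that gap.

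The importance is minor. The effect on this trial cannot be estimated from the documents. The simulation shows only that the exposure is real under its assumptions, and that a pre-set model or a choice blind to arm largely removes it.

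The conclusion rests on analysis still lying ahead when the SAP was written. Its analysis sections use the future tense, whereas data collection is described in the past tense. Changes to questionnaire collection are therefore a matter for the definitive trial.

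**What to change.** 1. Process accelerometer files under study number only, and write down the valid-wear and cut-point rules.
2. Build a pooled dataset without arm, visit dates or any other field that reveals arm, such as the intervention record log. On it, fix and sign off the valid-wear rule, scoring, transformations and covariate list.
3. In SAP Efficacy Analyses, delete the comparison of baseline differences between arms and the stepwise step. This is necessary because that rule cannot run on data without allocation. Replace it with the fixed list: baseline value and hospital, plus any prognostic covariates chosen without reference to arm.
4. Have the allocation code held by someone who makes none of these decisions, for example elsewhere in the trials unit that randomised, and join it after sign-off. The second statistician is a poor choice, because that person checks the outcome programs.
5. Rewrite SAP Randomisation and Blinding role by role: patients, class staff, outcome collectors, accelerometer processor, statistician. State how T1 and T2 questionnaires were completed.

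The cost is SAP wording and one extra sign-off before unmasking. For the definitive trial, consider separating outcome collection from the weekly log calls; that may need staff or a different collection route.

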## **Sample Size**

As this is a pilot RCT with embedded feasibility study, a formal power calculation is not appropriate; the study is not powered to detect a clinically meaningful difference in the primary outcome between the rehabilitation and usual care groups.

Rather the aim is to provide robust estimates of the likely rates of recruitment and retention, and to yield estimates of the variability of the primary and secondary outcomes to inform power calculations for a future large-scale trial. We will therefore use the pilot trial (Phase 2 of the proposed study) in order to provide a quantitative estimate of the intervention impact (relative to control) in order to inform the sample size estimation for a definitive trial.

For the pilot RCT (Phase 2), we believe that over 6 months across the 3 sites we will be able to approach 250 patients. From their responses we will be able to determine whether it is possible to recruit patients and also estimate eligibility, consent, participation and retention rates and speed of recruitment for a future large scale trial.

We have conservatively estimated that we will recruit approximately 66 patients. Cancer clinicians estimate that approximately one third will be ineligible (e.g. have advanced disease) and based on recruitment to a RCT about physical activity with cancer patients in Scotland (27% recruitment rate) and a trial involving colorectal cancer patients within 3 months of completing surgery conducted in Canada (35% recruitment rate) we estimate that about a third of eligible patients will consent. Thus, we estimate that in Site 2 and 3 26 patients in each site will be recruited (13 intervention group and 13 control group). In Site 1, we estimate that 14 patients will be recruited (7 intervention group and 7 control group). However, a recruitment rate of 71 per cent, which was achieved in a study of a personalised lifestyle programme for colorectal cancer survivors in Scotland would provide a total of 118 patients

